- Monitoring Phase: HPI 50 – 85 → evaluate flow / vascular tone indices and fluid responsive state.

Figure 1 : Treatment Protocol for Subjects Enrolled in the Treatment Arm

HPI Pressure & Flow Optimization Protocol

Note: Clinicians should validate the appropriateness of protocol recommendations, and provide treatment based upon their clinical judgment.

THIS DOCUMENT CONTAINS CONFIDENTIAL AND PROPRIETARY INFORMATION OF EDWARDS LIFESCIENCES, LLC. IT MAY NOT BE REPRODUCED OR DISCLOSED WITHOUT PRIOR WRITTEN PERMISSION FROM EDWARDS LIFESCIENCES, LLC.

Edwards Lifesciences, Edwards, the stylized E logo, HemoSphere, Acumen, Acumen IQ, FloTrac, and ForeSight Elite oximetry Sensor are trademarks of Edwards Lifesciences Corporation.

Randomization and Blinding

The randomization for this Trial will be implemented using an Interactive Web Response Systems (IWRS). The Sponsor will be blinded to the randomization codes. Participants will be randomized to either the control or treatment arm at enrollment. Study investigators will be blinded up until the time of the surgery. The clinician(s) involved in the consenting of the patient will be blinded to the randomization assignment and will not be involved in the care of the Trial subject. Once the intent of arterial line placement is confirmed with the anesthesia team, before surgery (the day before or in the morning of surgery), the subject will be randomized to either the treatment or control arm. The arterial line will then be placed. Randomization will be allocated in 1:1 ratio, stratified by site.

[figure not shown]

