7. STATISTICAL METHODS

Statistical Analysis Plan (SAP)

There will be a formal SAP, separate from this Trial protocol. A formal SAP will be completed prior to database lock and the analysis of any Trial endpoints data. The SAP will detail the planned statistical analyses. The subsections below summarize the planned analyses.

Primary Outcome Endpoint

The primary outcome endpoint is to determine if the use of a protocolized strategy using advanced hemodynamic monitoring with Hypotension Prediction Index (HPI) software guidance for intraoperative hemodynamic management reduces postoperative complication rate in moderate- to high-risk non-cardiac surgery. The composite includes MACE (myocardial injury, stroke, non-fatal cardiac arrest, and death), AKI, and serious infections (pneumonia, deep and organ space surgical site infections, and sepsis).

THIS DOCUMENT CONTAINS CONFIDENTIAL AND PROPRIETARY INFORMATION OF EDWARDS LIFESCIENCES, LLC. IT MAY NOT BE REPRODUCED OR DISCLOSED WITHOUT PRIOR WRITTEN PERMISSION FROM EDWARDS LIFESCIENCES, LLC.
Edwards Lifesciences, Edwards, the stylized E logo, HemoSphere, Acumen, Acumen IQ, FloTrac, and ForeSight Elite oximetry Sensor are trademarks of Edwards Lifesciences Corporation.

Sample Size Justification

The goal of this study is to assess if the use of Hypotension Prediction Index (HPI) software guidance impacts the incidence of postoperative morbidity and mortality in the adult population undergoing moderate-to-high-risk noncardiac surgery (with a pressure monitoring with an arterial line). A relative reduction in the composite outcome within the treatment arm is expected. For a group sequential analysis, following the O'Brien and Fleming methodology, a sample size was calculated for a two-sample comparison of rates (two-sided). The hypothesis are as follows:

$$H_0: p_0 - p_1 \geq 0$$

$$H_1: p_0 \neq p_1$$

Assuming at least a 25% relative change in rate for the treatment (p_1) arm, a type I error (0.05), a power of 80%, and a reference rate of 0.31 (p_0) based on a meta-analysis^{6,10,14}, a sample size of 1426 subjects are needed. An additional 60 subjects may be included as roll-ins, which results in a total enrollment potential of 1486 subjects.

Analysis Populations

Modified Intent-to-treat (mITT)

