Assuming a power of 80% and a relative reduction of at least 25% in the composite score (reference proportion=0.31) with three total looks (two interim analysis, one final), the critical values for each time point were chosen to preserve an overall type-1 error rate of 0.05. The O'Brien and Fleming methodology was used to determine the boundary rule for deciding when to stop the trial prematurely. Futility was included. A relative reduction in the composite outcome within the treatment arm is expected. The alpha at each interim and the maximum number of observations are chosen so that the overall significance level is the probability of detecting the treatment difference under the null hypothesis. The table below shows the critical values:

Analysis	Information Rate	Effectiveness Boundary z-value (Upper, Lower)	Futility Boundary z-value (Upper, Lower)
First Interim Analysis	50%	(2.96259, -2.96259)	(0.40273, -0.40273)
Second Interim	75%	(2.35898, -2.35898)	(1.12741, -1.12741)
Final Analysis	100%	(2.01404, -2.01404)	(2.01404, -2.01404)

THIS DOCUMENT CONTAINS CONFIDENTIAL AND PROPRIETARY INFORMATION OF EDWARDS LIFESCIENCES, LLC. IT MAY NOT BE REPRODUCED OR DISCLOSED WITHOUT PRIOR WRITTEN PERMISSION FROM EDWARDS LIFESCIENCES, LLC.

Edwards Lifesciences, Edwards, the stylized E logo, HemoSphere, Acumen, Acumen IQ, FloTrac, and ForeSight Elite oximetry Sensor are trademarks of Edwards Lifesciences Corporation.

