An adapted group sequential design will be utilized for this clinical study, and to determine stopping rules, or to re-estimate the sample size by interim analysis outcomes ^[10, 12, 14, 17]. Adapted group sequential study design allows for one or more planned interim analyses when a prespecified stopping criteria is chosen. If the first interim analysis outcomes provide evidence for the necessity to enroll more patients, study sample size will be reassessed to determine the new appropriate sample size ^[1,10]. When there is sufficient evidence from study data collected at present stage in addition to the data collected from previous study stage, the clinical trial could be stopped early for already achieving the study objectives. A type I error (α) spending function will be used to design stopping boundaries for effectiveness, while allowing flexibility in how many interim analyses are designed, and at what time point they are conducted ^[4]. The methodology from O'Brien, Harrington, and Fleming ^[16] will be used to determine the effectiveness stopping criteria for prespecified first interim analysis, the secondary interim analysis, and the final analysis with 50%, 75%, and 100% information respectively. Many literatures proposed different methodologies from weighted combining test statistics to weighted combining p value from interim analyses to preserve type I error (α). The O'Brien-Fleming methodology, the conservative approach, spend little type I error (α) at the time of interim analyses and lead to boundary values at the final stage that

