are close to those from fixed sample designs,¹⁶¹ The O'Brien-Fleming formulae (to preserve the familywise error rate, a) is denoted as follows, $\text{PH}_0(|Z_1| < c_1, \dots, |Z_k| < c_k) = a$, where $c_i = \text{cp}(K, a)$, where c_i represents the positive critical values corresponding to stopping boundaries and the trial stops at an interim-i where $|Z_i| \geq c_i$. In this clinical trial, the O'Brien-Fleming methodology will be used to split the type I error (a) for each interim analysis, and also used to calculate critical value to judge if receives or rejects the null hypothesis. If the Z-statistic is close to the critical boundary value but the null hypothesis could not be rejected. By adapted group sequential study design principles, the study sample size will be re-assessed for the purpose to achieve the study objective by a third-party, independent, un-blinded statistician who will not unblind the study statistician and hence does not involve an alpha penalty. It is noted that a group sequential design with one(50%) interim analysis can reduce the expected sample size of a clinical trial by roughly 15%^{13, 11, 171}.

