 Edwards	Revision Date: May 11, 2022		Rev	A	For Use Only by Affiliates of Edwards Lifesciences	Page 6 of 19
	Title	Statistical Analysis Plan for HP/ SMART-BP Trial				

estimation, and is supported by the integrated evidence from physician clinical experience, scientific publications, and previous clinical trial results.

The hypothesis setting for this study used in sample size estimation is:

$H_0: P_1 \geq P_0$

$H_1: P_1 < P_0$

where p_1 and p_0 are the proportions of composite endpoint in treatment arm and control arm, respectively.

Moreover, two interim analyses will be designed at 50% and 75% subject enrollment with 30-day follow-up data, to assess the composite endpoint (pooled event rate) between treatment and control arms. To determine when the trial can be stopped prematurely for effectiveness, the O'Brien-Fleming methodology¹⁶ was used to determine the stopping boundary (alpha spending function). The O'Brien-Fleming methodology preserves the overall type I error across all interim analyses¹⁶. The overall type I error used for this one tail hypothesis test study is 0.025. If the Z-statistics is close to boundary value but could not reject null hypothesis, possibly the study sample size will be reassessed for the purpose to achieve study objective.

With these trial parameter and hypothesis settings, and two designed interim analyses plus a final analysis, 1486 subjects (including 15% attrition, including a maximum of 60 roll-ins) are needed for this clinical trial. The sample size is estimated with PASS2021. The critical Z value and the corresponding p value for effectiveness boundary are displayed in the following table for interim analysis and final analysis. By the study objective and experiment design, in effectiveness analysis if the Z value calculated by the data available at each study stage (interim analysis and final analysis) is less or equal the critical Z value listed in effectiveness boundary column, the null hypothesis will be rejected, and the study stops for the study objective is achieved. To simplify the interim analysis decision making procedure, the lower limit of the reference arm accumulated subjects with complication, and the upper limit of treatment arm accumulated subjects with complication are designed by the study design parameters, the study arm accumulated sample size at each analysis stage, and effectiveness boundary (critical Z value) estimated by O'Brien-Fleming methodology.

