By the study designed parameter table in section 2.3 and the Z statistic calculated at each study stage with the trial data collected at present stage in addition to data collected in previous stage or stages, following judgement will be conducted for interim analysis and final analysis. For first and second interim analyses, if the calculated Z value is equal to or less than the critical Z value in the effectiveness boundary column, the null hypothesis will be rejected, and the study will stop for achieving the study objective; if the calculated Z statistic is greater than critical Z value for effectiveness but it is close to the critical value but could not reject null hypothesis, the study continues to next step, and the study sample seize will be reassessed by the principles of adapted group sequential study design. If it is necessary, more study subject will be enrolled for the purpose to achieve the study objectives. For final analysis, if the calculated Z statistic is equal to or less than the critical Z value listed in effectiveness boundary column, the null hypothesis will be rejected, and the alternative hypothesis will accept, the study objective is achieved, otherwise, the null hypothesis will accept, the study objective will be not achieved.

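### The SAP's claim of no alpha penalty for unblinded sample-size re-estimation does not follow from the firewall, and the rule is too open to guarantee one-sided 0.025

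*Combined protocol and SAP*

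**What the plan says.** SAP 2.2 describes an adaptive group sequential design with looks at 50%, 75% and 100% information. If Z falls short of the boundary but close to it, N may be reassessed by an independent unblinded statistician "who will not unblind the study statistician and hence does not involve an alpha penalty". The same section notes that weighted test statistics and weighted p-values exist in the literature, but adopts neither.

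SAP 8.1 applies the trigger at both interim looks, when Z misses the critical value but "it is close to the critical value but could not reject null hypothesis". It calculates Z from the current data together with all earlier data and compares it with the critical values in SAP 2.3, which do not change if N does. SAP 2.2 mentions only one look by name: "If the first interim analysis outcomes provide evidence for the necessity to enroll more patients".

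SAP 2.3 sets the error rate: "The overall type I error used for this one tail hypothesis test study is 0.025". No section gives a numerical trigger zone, a target conditional power, a re-estimation formula or a maximum N after an increase. Protocol section 7 (Planned Interim Analyses) lists futility bounds but does not mention re-estimation. The SAP boundary table lists no futility bounds.

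**The concern.** The SAP infers control of type I error from who sees the data. These are separate matters. Keeping the study statistician blinded limits operational bias. It does not change the null distribution of the final Z, which shifts whenever N is chosen from the unblinded interim Z and all patients then receive equal weight. With the ordinary Z, alpha is protected only if increases are confined to a suitable zone. With a fixed-weight statistic, it is protected for any increase. The SAP commits to neither.

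If N were increased, the primary result would rest on a justification that does not hold and a rule that was not fixed before unblinded data were used. It could be challenged on that ground even if the increase actually made was harmless.

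**Working it through.** **Inputs.** Boundaries |Z| = 2.96259, 2.35898, 2.01404 at information 0.50, 0.75, 1.00 (SAP 2.3 and protocol section 7). Overall one-sided alpha 0.025 (SAP 2.3); the protocol's two-sided 0.05 uses the same upper boundary. Futility bounds 0.40273 and 1.12741 (protocol section 7). Planned power 80%. Z is taken as positive in the direction of benefit.

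**Step 1: the plan's own figure.** Lan-DeMets O'Brien-Fleming-type spending at one-sided 0.025 gives 2.9626 / 2.3590 / 2.0141. The SAP boundaries spend 0.00153 + 0.00812 + 0.01535 = 0.0250. With N fixed, alpha is controlled.

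**Step 2: why a change of N matters.** At the second look (t = 0.75), the null chance of a final rejection given Z, if N is multiplied by f, is

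1 − Φ[(2.01404·√f − Z·√t) / √(f − t)].

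- Z = 1.0: at f = 1, (2.01404 − 0.86603)/0.5 = 2.296, giving 0.011. At f = 2, (2.84828 − 0.86603)/1.11803 = 1.773, giving 0.038. Doubling N raises the null rejection chance.
- Z = 1.744: at f = 1, (2.01404 − 1.51035)/0.5 = 1.007, giving 0.157. At f = 2, (2.84828 − 1.51035)/1.11803 = 1.197, giving 0.116. Doubling N lowers it.

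The direction depends on where the interim Z lies, not on who calculates it.

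**Step 3: conditional power at planned N, current trend.** CP = Φ[(Z/√t − 2.01404)/√(1 − t)]. CP is 50% at Z = 2.01404·√t, which is 1.424 at the first look and 1.744 at the second. CP is 80% at Z = 1.845 and 2.109.

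- First look: CP is 99.5% at 0.25 below the boundary and 98.1% at 0.5 below.
- Second look: CP is 80% at 0.25 below and 60% at 0.5 below. With N × 1.5 these rise to 91% and 81%.

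**Step 4: overall alpha by numerical integration, boundaries unchanged.** The SAP gives no zone and no size of increase, so both are assumptions. The first four rows assume no futility stopping.

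| Assumed rule | Alpha |
|---|---|
| First look, within 0.5 of boundary, N × 1.5–2 | 0.0236–0.0248 |
| Second look, within 0.25 / 0.5 / 1.0 of boundary, N × 2 | 0.023 / 0.022 / 0.021 |
| CP 50–80%, N × 1.5–2, first look; second look | 0.0237–0.0243; 0.0229–0.0236 |
| CP below 50% (Z from 0 up), N × 1.5–2, first look; second look | 0.028–0.029; 0.030–0.032 |
| N chosen to maximise rejection, first look, cap 2x; 4x | 0.031; 0.035 |
| Same, second look, cap 2x; 4x | 0.033; 0.038 |
| Same, protocol futility bounds always followed, first look, cap 2x; 4x | 0.026; 0.027 |
| Same, futility followed, second look, caps 1.5x to 4x | 0.025 |

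The worst cases for the first look assume that the second look moves to 75% of the new N. With futility followed and no increase, alpha is 0.0234.

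**Step 5: gain in power.** From a planned 80%, increasing N by 1.5 to 2 times within 0.5 of the first boundary adds 0.2 to 0.3 points. In the CP 50–80% zone, the same increase adds about 2 to 3 points at either look.

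**The case against.** The best defence is that the conclusion is numerically right on an ordinary reading of the trigger. An increase made only near the boundary does not inflate alpha; it lowers it slightly. Even a trigger running well down from the second boundary need not inflate overall: within 1.0 at N × 1.5 gives 0.0226, and inflation appears only with a much wider zone (within 2.0 gives 0.0268). The protocol's futility bounds remove most of the harmful region. Large caps are also remote: four times 1426 is 5704 subjects, the protocol allows up to 1486, and its section 14 requires an IRB-approved amendment for such a change. All of this stands, and it limits the size of the problem.

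It does not rescue the SAP's reason. The SAP does not say that close means a zone with high conditional power, does not call the futility bounds binding, and omits them from its own table. Its reference list includes papers on increasing N when interim results are promising, but a citation is not a pre-specified rule.

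A reader might infer that the trigger must either gain nothing or inflate alpha. The calculations contradict this: the CP 50–80% zone adds power with alpha below 0.025. A reader might also infer that the trigger is misplaced in general. That is so only near the first boundary; near the second, an increase can be useful. Nor does alpha control require re-estimation to be confined to the first look.

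**Conclusion.** The point stands in a limited form. The no-penalty justification is invalid, and the rule is too loosely specified for the stated 0.025 to be guaranteed. The documents do not show that alpha would in fact be inflated. If increases stay close to the boundary, or at conditional power of at least 50%, alpha is about 0.021 to 0.025 for N × 1.5 to 2. Without futility stopping, increases at lower conditional power give about 0.028 to 0.032, and the worst-case choice of N gives 0.031 to 0.035 at the first look and 0.033 to 0.038 at the second (caps 2x to 4x). With the futility bounds always followed, the worst cases are about 0.026 to 0.027 and 0.025. Every figure for an increased N rests on an assumed zone and increase, because the SAP states neither.

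SAP 2.2 and 8.1 do not flatly contradict each other on timing, since 2.2 does not say only the first look, but they should be made to agree.

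**What to change.** In SAP 2.2, delete the claim that no alpha penalty arises. The firewall itself should stay. Then adopt one of two rules.

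1. **Fixed weights (Cui-Hung-Wang / inverse normal).** If N is increased, combine the stage-wise Z values with weights set by the planned information fractions: at the second look (√0.50·Z1 + √0.25·Z2)/√0.75, and at the final analysis √0.50·Z1 + √0.25·Z2 + √0.25·Z3. Compare these with the existing boundaries. Alpha then holds whatever increase is chosen.
2. **Ordinary Z with a floor.** Allow an increase only when conditional power at the planned N is at least 50% (|Z| at least about 1.42 at the first look, 1.74 at the second), with a stated maximum N.

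State in both 2.2 and 8.1 at which look or looks the rule applies.

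The cost is SAP wording and a few lines of code. The weighted statistic is slightly less efficient if N is increased.

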2.3 Sample Size Consideration

Meta-analysis approach is used to optimally integrate the valid information collected from literature. Here, the statistics (pooled effect sizes (ES)) from the meta-analysis construct the composite endpoint for the reference (control) group. Composite endpoint is comprised of the following components: (1) MACE (myocardial injury¹²¹, stroke, non-fatal cardiac arrest, and death), (2) AKI (KDIGO stage 2-3), and (3) infection (pneumonia, deep surgical site, and organ space surgical site).

The event rate (pooled effect size) of the control arm to be given is 0.31. This event rate was calculated using the weighted average methodology where the final event rate is based on the sample sizes as the weight from following manuscripts, Futier et al.¹⁷¹, Pearse et al.¹³¹, and Maheshwari et al.¹⁹¹. The algorithm formula is: $ES = \frac{\sum w_i \cdot e_i}{\sum w_i}$. Moreover, for manuscripts in which individuals who experienced MINS, stroke or death simultaneously were observed, an adjustment was conducted so that there is no overcounting within the meta-analysis. The event rate for the components MACE, AKI, and infection is as 0.06788, 0.10217, and 0.17182 respectively. Please see algorithm listed below the table using in the meta-analysis and final composite endpoint computation.

Sample Size	• • • •			AKI(%)	Infection (%)		
	■	■	■		Renal	Deep Surgical Site	Organ Space Surgical Site
n=145	■	■	■	6.5	17.9	0	24.8
n=364	■	■	■	3.0	4.7	01	9.9
n=108	■	■	■	(J:1)3	18.5	31.5 ³	0
Composite	6.288			10.217	17.182		

$$\text{Compilation Composite} = 1 - (1 - 0.06788) * (1 - 0.10217) * (1 - 0.17182) = 0.30690$$

Although there are other derivations of the meta-analysis including Fleiss's inverse variance methodology¹⁵¹ (Please see appendix section 12.1, 12.2, and 12.3), this conservative control arm final composite endpoint estimate (0.31) is selected to estimate sample size for this clinical trial, due to this being more reflective of what is observed in clinical practice. A 25% reduction of the composite endpoint by the treatment arm is expected for this trial, which is used in sample size

¹ Did not report deep alone, this statistic was merged with other infection types.

² MINS rate was adjusted for overcounting, original rate for MINS 7/108 (6.7%) 5/108 (4.6%)

³ Deep Surgical Site Infection rate was adjusted for overcounting, original rate 35/108 (32.4%) 34/108 (31.5%)

 Edwards	Revision Date: May 11, 2022		Rev	A	For Use Only by Affiliates of Edwards Lifesciences	Page 6 of 19
	Title	Statistical Analysis Plan for HP/ SMART-BP Trial				

estimation, and is supported by the integrated evidence from physician clinical experience, scientific publications, and previous clinical trial results.

The hypothesis setting for this study used in sample size estimation is:

$H_0: P_1 \geq P_0$

$H_1: P_1 < P_0$

where p_1 and p_0 are the proportions of composite endpoint in treatment arm and control arm, respectively.

Moreover, two interim analyses will be designed at 50% and 75% subject enrollment with 30-day follow-up data, to assess the composite endpoint (pooled event rate) between treatment and control arms. To determine when the trial can be stopped prematurely for effectiveness, the O'Brien-Fleming methodology¹⁶ was used to determine the stopping boundary (alpha spending function). The O'Brien-Fleming methodology preserves the overall type I error across all interim analyses¹⁶. The overall type I error used for this one tail hypothesis test study is 0.025. If the Z-statistics is close to boundary value but could not reject null hypothesis, possibly the study sample size will be reassessed for the purpose to achieve study objective.

With these trial parameter and hypothesis settings, and two designed interim analyses plus a final analysis, 1486 subjects (including 15% attrition, including a maximum of 60 roll-ins) are needed for this clinical trial. The sample size is estimated with PASS2021. The critical Z value and the corresponding p value for effectiveness boundary are displayed in the following table for interim analysis and final analysis. By the study objective and experiment design, in effectiveness analysis if the Z value calculated by the data available at each study stage (interim analysis and final analysis) is less or equal the critical Z value listed in effectiveness boundary column, the null hypothesis will be rejected, and the study stops for the study objective is achieved. To simplify the interim analysis decision making procedure, the lower limit of the reference arm accumulated subjects with complication, and the upper limit of treatment arm accumulated subjects with complication are designed by the study design parameters, the study arm accumulated sample size at each analysis stage, and effectiveness boundary (critical Z value) estimated by O'Brien-Fleming methodology.

Analysis	Information Rate	Alpha Spending Function	Effectiveness Boundary Critical Z value	P-Value
First Interim	50%	O'Brien-Fleming	-2.96259	0.00153
Second Interim	75%	O'Brien-Fleming	-2.35898	0.00916
Final Analysis	100%	O'Brien-Fleming	-2.01404	0.02200

Analysis	Information Rate	Proportion of Control Subject with Complications	Required Reduction Rate	Control Arm Limit (2::)	Treatment Arm Limit (<)	Subject Ratio(<)*
First Interim	50%	0.31	0.33	111	74	0.67
Second Interim	75%	0.31	0.21	167	131	0.78
Final Analysis	100%	0.31	0.16	222	186	0.84

Note: * Subject Ratio = Treatment Arm Limit / Control Arm Limit.

 Edwards	Revision Date: May 11, 2022		Rev	A	For Use Only by Affiliates of Edwards Lifesciences	Page 7 of 19
	Title	Statistical Analysis Plan for HPI SMART-BP Trial				

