Here x_0 and x_1 are the amount of events that occurred in the reference arm and test arm respectively, thus, $\hat{p} = \frac{x_0}{n_0}$, $\hat{p} = \frac{x_1}{n_1}$ are the proportion of events that occurred in the reference arm and test arm, respectively, n_0, n_1 are the number of subjects in reference arm and test arm respectively. The pooled standard error is given by $\sqrt{\frac{(x_0+x_1)}{n_0+n_1}(1 - \frac{x_0+x_1}{n_0+n_1})(\frac{1}{n_0} + \frac{1}{n_1})}$. The z-statistic will be calculated using data from the complete case population and it will be compared to the critical z-value ($z(\alpha', n_0 + n_1 - 2)$) to judge if the null hypothesis can be rejected. Here α' is the adjusted type I error rate (adjusted for interim analysis). Moreover, the degree of freedom is given by, $n_0 + n_1 - 2$. The 95% CI is given by $\hat{p} - \hat{p} \pm z_{\alpha} \sqrt{\frac{(x_0+x_1)}{n_0+n_1}(1 - \frac{x_0+x_1}{n_0+n_1})(\frac{1}{n_0} + \frac{1}{n_1})}$. The other analysis methods are detailed in the statistical analysis plan.

Additional Evaluations

The continuous variables will be evaluated using the parametric two sample t-test (or the Welch t-test if unequal variance or the Wilcoxon-Mann Whitney test if non-normally distributed) and categorical/binary variables will be evaluated using a chi-squared test (Fisher's exact if low counts). Logistic regression will be used to evaluate incidence of AKI with other variables being used as co-variates. Time-to-event variables will be evaluated by survival analysis models (Kaplan-Meier or Cox Proportional Hazards). Summary statistics and statistical comparison will be presented in tables with point estimates (odds ratios or log odds), standardized errors, and 95% CI. There will be no multiplicity adjustment for performing multiple hypothesis tests of exploratory outcomes, unless specified otherwise.

Sensitivity analysis including the review of any influence of surgical position, type of anesthesia, tidal volume etc., on the primary outcome measure, are specified in the SAP.

The following data will also be explored:

1. Time-to-Adverse Event (Complications) Analysis
 - a. Non-Parametric Survival Analysis (KM approach)
 - b. Cox Proportional Hazard Model
 - c. Mixed effect Cox Proportional Hazard Model
 - d. Stratification analysis through applying study sites, gender, race as the stratification factor
 - e. Fixed/Mixed effective Poisson regression model applying the count of events as the response

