8. STATISTICAL ANALYSIS OF STUDY ENDPOINTS

8.1 Primary Effectiveness Endpoint

The primary objective is to determine if the use of a protocolized strategy using advanced hemodynamic monitoring with Hypotension Prediction Index (HPI) software guidance for intraoperative hemodynamic management reduces postoperative complication rate in moderate- to high-risk non-cardiac surgery patient. The treatment group (Acumen ID sensor) will be compared to control arm receiving standard of care (FloTrac sensor). This analysis will be conducted on the mITT population only with pivotal study subject. With null hypothesis, the Z-statistic will be used to judge if the hypotension prediction index software can reduce postoperative morbidity and mortality:

$$Z = \frac{\hat{p}_0 - \hat{p}_1}{\sqrt{\frac{\hat{p}_0(1-\hat{p}_0)}{n_0} + \frac{\hat{p}_1(1-\hat{p}_1)}{n_1}}}$$

Here x_0 and x_1 are composite endpoint events in the reference arm and treatment arm respectively; thus, $\hat{p}_0 = \frac{x_0}{n_0}$, $\hat{p}_1 = \frac{x_1}{n_1}$ are the proportion of events in the reference arm and treatment arm, respectively; n_0 , n_1 are the number of subjects in

 Edwards	Revision Date: May 11, 2022	Rev	A	For Use Only by Affiliates of Edwards Lifesciences	Page 13 of 19
	Title	Statistical Analysis Plan for HPI SMART-BP Trial			

reference arm and treatment arm respectively; $\frac{\hat{p}_0*(1-\hat{p}_0)}{n_0}$, $\frac{\hat{p}_1*(1-\hat{p}_1)}{n_1}$ is the variances of the proportion of events in reference arm (\hat{p}_0), and in test arm (\hat{p}_1) respectively. The Z-statistic will compare to the critical Z-value to judge if the null hypothesis could be rejected.

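### The fixed event-count limits in SAP 2.3 are not equivalent to the Z rule they are meant to simplify, and the SAP never says they are non-decisional

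*Combined protocol and SAP*

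**What the plan says.** SAP 2.3 states the efficacy rule in Z: the null is rejected "if the Z value calculated by the data available at each study stage (interim analysis and final analysis) is less or equal the critical" value in the effectiveness boundary column (-2.96259, -2.35898 and -2.01404 at 50%, 75% and 100% information). The next sentence begins "To simplify the interim analysis decision making procedure, the lower limit of the reference arm accumulated subjects with complication" and pairs this with an upper limit for the treatment arm. It says the limits are "designed by the study design parameters, the study arm accumulated sample size at each analysis stage, and effectiveness boundary (critical Z value"). No variance is named.

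A second table then prints the limits for an assumed control rate of 0.31:

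| Look | Required reduction | Control (at least) | Treatment (below) | Ratio (below) |
|---|---|---|---|---|
| 50% | 0.33 | 111 | 74 | 0.67 |
| 75% | 0.21 | 167 | 131 | 0.78 |
| 100% | 0.16 | 222 | 186 | 0.84 |

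Its footnote is "Subject Ratio = Treatment Arm Limit / Control Arm Limit".

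SAP 8.1 uses an unpooled statistic: "The Z-statistic will compare to the critical Z-value to judge if the null hypothesis could be rejected". Protocol section 7 uses a pooled one ("The pooled standard error is given by" a formula in the combined event proportion). The decision paragraph in SAP 8.1 opens "By the study designed parameter table in section 2.3 and the Z statistic calculated at each study stage" and then stops the trial at an interim "if the calculated Z value is equal to or less than the critical Z value in the effectiveness boundary column".

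**The concern.** A table offered to simplify the interim decision should give the same answer as the rule it stands for. A two-proportion Z depends on both observed proportions and both denominators. Fixed counts can match it only at one control rate and one pair of arm sizes.

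The SAP does not say how the two limits and the ratio column combine, whether the limits are recomputed for the actual arm sizes, or that the counts are only illustrative. If the unblinded statistician or the DSMB read the decision from this table, the trial could keep randomising after its stated efficacy boundary had been crossed.

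**Working it through.** **Inputs.** Control rate 0.31 and a 25% reduction, so 0.2325 on treatment (SAP 2.3). Allocation 1:1 (SAP 2.4). Pivotal N 1426 (protocol section 7), so 713 per arm and about 357 and 535 per arm at the interims. Critical |Z| 2.96259, 2.35898, 2.01404 (SAP 2.3). The control column's inequality sign is damaged in the public text; it is read as at or above, because SAP 2.3 calls it a lower limit.

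**1. Reproducing the printed limits.** Required reduction = c × √(2 × 0.31 × 0.69 / n) / 0.31. Control limit = 0.31n rounded up. Treatment limit = control limit × (1 − reduction), rounded down.

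| n per arm | Reduction | 0.31n, control limit | Treatment limit |
|---|---|---|---|
| 358 | 0.3304 | 110.98, 111 | 111 × 0.6696 = 74.3, 74 |
| 537 | 0.2148 | 166.47, 167 | 167 × 0.7852 = 131.1, 131 |
| 716 | 0.1588 | 221.96, 222 | 222 × 0.8412 = 186.7, 186 |

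All six limits are recovered. The final size is not unique: 715 per arm gives the same six, and so does 714 with interim sizes rounded up. The protocol's 713 does not, since 0.31 × 535 = 165.85 gives a second control limit of 166. The variance behind the limits is 0.31 × 0.69 in both arms, which is neither the unpooled form in SAP 8.1 nor the pooled form in the protocol.

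**2. Effect of the variance alone.** With 111/167/222 control events at 357/535/713 per arm, the SAP 8.1 statistic still crosses at up to 76/132/187 treatment events (|Z| 2.998/2.391/2.052). The pooled form gives the same counts. This gap is small and conservative.

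**3. Effect of fixing the counts.** The control limit sits at about the expected count. At a true rate of 0.31 the binomial chance of missing it is 49.5%, 52.7% and 51.7% at 357, 535 and 713 per arm. Z carries no such condition. For 120 v 80 at 357 per arm: 0.3361 − 0.2241 = 0.1120; standard error = √(0.3361 × 0.6639/357 + 0.2241 × 0.7759/357) = 0.03335; |Z| = 3.36.

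| Per arm | Control v treatment | \|Z\| | Boundary | Limit failed |
|---|---|---|---|---|
| 357 | 120 v 80 | 3.36 | 2.963 | treatment (80 not below 74) |
| 357 | 105 v 65 | 3.55 | 2.963 | control (105 under 111) |
| 535 | 180 v 140 | 2.68 | 2.359 | treatment (140 not below 131) |
| 535 | 160 v 122 | 2.65 | 2.359 | control (160 under 167) |

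**4. Operating characteristics.** Control rate 0.31, treatment rate 0.2325, looks at 357/535/713 per arm, equal arms, efficacy stopping only, Z at the final look in every row. The type I error column uses 0.31 in both arms.

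| Rule at the interims | Stop at first | Stop at either | Expected total N | Power | Type I error |
|---|---|---|---|---|---|
| Z | 26.9% | 69.6% | 1083 | 90.5% | 2.5% |
| Both count limits | 5.9% | 36.2% | 1276 | about 90.1% | 2.2% |
| Ratio column only | 18.9% | 65.4% | not computed | 90.4% | 2.3% |

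When Z crosses, the two limits are not both met in 78% of trials at the first interim and 50% at the second. If the treatment limit means at or below, 36.2% becomes 38.0%. Over an assumed control-rate range of 0.29 to 0.33, early stopping by Z v both limits is 65% v 16% at 0.29 and 74% v 35% at 0.33.

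**5. Direction.** At equal planned arms, the smallest |Z| that satisfies both limits is 3.276, 2.534 and 2.173 at the three looks, each beyond its boundary. So the counts never cross when Z does not. Slight imbalance breaks this: 111/364 v 73/349 meets both limits, but |Z| = 2.947 is short of 2.963.

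**6. Sign.** SAP 8.1 prints the numerator as control minus treatment, so benefit gives a positive Z (111/357 v 73/357 gives +3.28), while rejection requires Z at or below a negative value. The calculations above use the magnitude in the direction of benefit.

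**The case against.** The strongest reply is that there is only one rule. Every rejection clause in SAP 2.3 and 8.1 is written in Z, and no sentence stops the trial because the counts are met. The opening reference in 8.1 to a parameter table is vague, since 2.3 has two tables, but its decision clauses name the effectiveness boundary column, which only the critical-Z table has. This largely stands: Z is the natural reading. What remains is a printed set of thresholds, offered expressly for the interim decision, that gives different answers and carries no label.

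The size of the effect also depends on a reading the SAP does not state, and on the ratio-only reading it is slight. Treating the protocol's futility boundary as binding changes the absolute figures (power 89.2% v 88.8%, expected N 1055 v 1249) but not the contrast.

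Four stronger inferences are tempting and not supported:

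- That the trial could move to sample-size reassessment after Z has crossed. The SAP makes reassessment conditional on Z not rejecting.
- That power falls to about 53%. That needs the counts to govern every look, including the final one, where 8.1 decides on Z.
- That type I error is inflated. It is not at equal planned arms, and the imbalance example shows only that the two rules can disagree in that direction.
- That the limits were built on 716 per arm. No document says so, and 714 or 715 serve as well.

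**Conclusion.** The point holds as a defect of specification. The count limits are not equivalent to Z, and the SAP does not say they are non-decisional. With both limits in place of Z at the interims, under the step 4 assumptions, the chance of early stopping roughly halves and expected enrolment rises by about 193 subjects (1276 − 1083). With equal planned arms the harm is delayed stopping, not a false positive claim. It arises only if staff use the counts in place of the Z rule that the SAP states. It is worth correcting before the first unblinded look, because a clarification made afterwards would be open to challenge.

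**What to change.** Delete the count-limit table from SAP 2.3. Alternatively, label it illustrative and non-decisional, valid only for a 0.31 control rate and equal planned arms, with the sponsor stating the per-arm sizes and variance it actually used. Replacing the limits with corrected counts is not enough: 76 and 132 used jointly would bring early stopping back only to about 40%.

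State in SAP 2.3 and 8.1 that at every look only Z, computed with the actual denominators in each arm, is compared with the critical-Z table, and point the opening reference in 8.1 to that table by name. In the same sentence define Z as treatment minus control, or make the boundaries positive and reverse the inequality.

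The cost is one table deleted or relabelled and a sentence edited in each of the two sections. Sample size, boundaries and trial conduct do not change.
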